4.2. Scope and Duration of the Clinical Study

Study enrollment started in the United States in 2015. Up to ten (10) investigational sites may participate. The enrollment period is estimated to be 20 months. To ensure adequate disease state representation for analysis, a minimum of approximately 25% of the subjects will be enrolled for the treatment of aneurysms or penetrating ulcers and a minimum of approximately 25% of the subjects will be enrolled for the treatment of chronic Type B dissections.

VML_Eval Statistical Analysis Plan **Form** Medtronic Revision [6.0] Page 6 of 27

Data from the presently treated subjects (planned up to 44) who undergo treatment with the Valiant Mona LSA Thoracic Stent Graft System in this study will be analyzed and summarized in Annual Progress Reports (APR) for FDA. Data collected in this study may be further used to submit original marketing applications for approval to commercially distribute the device system.

To permit collection of long-term safety and effectiveness data on the stent graft system, subjects will be followed for a total of 5 years under this same clinical protocol. After the scheduled 12-month study visit, patients will continue to be evaluated on an annual basis for up to 5 years post implantation. When all enrolled subjects have been followed for 5 years post index procedure, or have exited, the study will be closed.

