7.9.3. Additional Observations

7.9.3.1. Major Adverse Events and Major Clinical Events

The following observations will be assessed through clinical follow-up (office visit or phone contact):

- Major adverse events (MAEs) rates within 30 days of the initial or secondary procedures, including:
 - All-Cause Mortality
 - Myocardial Infarction
 - Paraplegia
 - Renal Failure
 - Stroke
 - Left Arm/Hand Ischemia
- Secondary endovascular procedures
- Rupture
- Conversion to surgery
- Surgical revascularization of the LSA
- **Paraparesis**

[figure not shown]
The rate of the above events will be calculated on the subject level, and for different reporting time points, the correspondent cutoff days will be used as shown in Table 3.

For each visit (or reporting time point), the event rate will be calculated as the proportion of the number of subjects with a certain event term over the number of evaluable subjects. The evaluable subjects at each reporting time point include all subjects who are enrolled by the snapshot date and

- 1) Had a clinical or safety event (e.g. MAE) within (on or before) the Reporting cutoff Days, or
- 2) Had a follow-up or days to last contact at or after the lower limit of the Reporting Window,

Revision [6.0]

Page 19 of 27

[figure not shown]
3) The Withdrawal Consent Date /Recorded Lost-to-Follow-up Date at or after the lower limit of the Reporting Window

'Days to MAE' (date of earliest MAE – date of index procedure) and 'Days to Last Contact' (date of last contact – date of index procedure) are usually used for the determination of the eligibility of the 'evaluable subject'. The last contact date will be calculated based on the information gathered from all available dates during the follow-ups.

Similarly, 'Days to any AEs' and 'evaluability' of any AEs will be determined with the same principle as described above.

- 1. For death, Use the date of death from the CEC form, if it is not available then use Date of Death from study exit form.
- 2. For withdrew ("Subject withdrew consent to participate in the study" or " Physician's decision to protect the welfare of the subject") or "Subject enrolled but not implanted, completed 1 month follow-up", use Date of Exit from study exit form.
- 3. For patients who exited study for LTF, complete FU, or other reason, use last known date in the study from:
 - 1) Adverse Event Form
 - (i) Date event started
 - (ii) Date of resolution
 - 2) Secondary Procedure Form: Date of secondary procedure

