7.9.4. Subset Analysis

Subset analyses of the primary safety and effectiveness observations will be created for the subjects enrolled with aneurysms, penetrating ulcers, or chronic Type B dissections. Descriptive statistics will be used to analyze the primary observations, additional observations, and periprocedural and discharge clinical utility measures.

7.10.Safety Evaluation

Any Adverse events (AEs or SAEs) other than MAEs will be summarized by relationship and time period. Relationship will be site-reported in 3 categories, device-related, procedure-related and aneurysmrelated. If an AE is in 2 or more categories, it will be included in both or all summaries. All SAEs will be summarized separately. All AEs will be coded according to the Medtronic Endovascular Dictionary.

The rate of any AE will be calculated for following time periods:

- 0-30 days
- 31-365 days
- 366-730 days
- 731-1095 days
- 1096 -1460 days
- 1461 1825 days

The event rate is determined by number of subjects who had the event during the time period divided by number of subjects at risk at the beginning of the time period, i.e. number of subjects who are still in the study at the beginning of the time period.

Unanticipated Serious Adverse Device Effects (USADEs), Unanticipated Adverse Device Effects (UADEs) and deaths will be provided in a listing. Device malfunctions and failures will be listed.

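### Section 7.10 counts subjects who are only part-way through a period as event-free for all of it, so snapshot AE rates run low; for Days 0-30 it also clashes with the evaluability rule in 7.9.3.1

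*SAP*

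**What the plan says.** SAP 7.10 (Safety Evaluation) covers the adverse events outside the MAE list: "Any Adverse events (AEs or SAEs) other than MAEs will be summarized by relationship and time period". It then states that "The rate of any AE will be calculated for following time periods" and lists Days 0-30, 31-365, 366-730 and so on to Day 1825. The numerator is the "number of subjects who had the event during the time period". This is "divided by number of subjects at risk at the beginning of the time period", which the section explains as the "number of subjects who are still in the study at the beginning of the time period". No minimum observation within the period is required, and subjects who have not yet completed it are not treated separately.

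SAP 7.9.3.1 uses a different denominator for MAEs and the listed major clinical events: "the number of subjects with a certain event term over the number of evaluable subjects". A subject is evaluable if an event occurred by the reporting cutoff, or if last contact, withdrawal or loss to follow-up falls at or after a lower limit in Table 3 (Day 15 for the Day 30 cutoff, Day 335 for the Day 365 cutoff). The section then adds that days to event and evaluability "of any AEs will be determined with the same principle as described above".

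SAP 4.2 plans about 20 months of enrolment and up to 44 subjects, whose data "will be analyzed and summarized in Annual Progress Reports (APR) for FDA". The study closes only when every subject has reached five years or exited.

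**The concern.** Entry is staggered and reports are made yearly, so some reports will be cut while subjects are part-way through a period. Under 7.10, a subject who entered the Day 31-365 period a week before the snapshot carries the same weight as one who completed it without an event. That amounts to assuming no event in the unobserved remainder, although 7.4 says missing data will in general not be imputed. The error favours the device, and it recurs in each later annual period until the last subject has passed it.

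The study is descriptive, so these rates are themselves the result. They go to the regulator each year, and 4.2 says the data may support a marketing application. Separately, a programmer can find two instructions for the denominator of an AE rate and no statement of which governs.

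**Working it through.** The SAP gives no AE rate, power or sample-size figure, so there is no plan figure to reproduce.

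**Inputs.** From the SAP: 20 months of enrolment (about 608 days); the 7.10 periods; the Table 3 limits. Assumed, because the documents give none: uniform accrual, constant hazard, the true period risk R, and the fraction leaving early. Section 7.1.1.1 describes staged enrolment, so actual accrual need not be uniform.

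**Formula.** Scale the period to length 1 and let λ = -ln(1-R). A subject observed for a fraction u of the period shows an AE with probability 1 - exp(-λu). If a fraction p of entrants have completed the period and the rest are observed for U uniform on (a, 1), then

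- expected 7.10 rate = p·R + (1-p)·E, where E = 1 - [exp(-λa) - exp(-λ)] / [λ(1-a)].

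**Days 31-365, snapshot at month 20 (Day 608), no dropout.** Follow-up is uniform on 0-608 days. Those past Day 30 span 578 days, so p = (608-365)/578 = 0.420, 1-p = 0.580 and a = 0.

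- R = 30%: λ = 0.3567; E = 1 - 0.30/0.3567 = 0.159; rate = 0.420×0.30 + 0.580×0.159 = 0.218.
- R = 10%: λ = 0.10536; E = 1 - 0.10/0.10536 = 0.0509; rate = 0.420×0.10 + 0.580×0.0509 = 0.072.

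**Same period, snapshot at month 24 (Day 730).** Follow-up is uniform on 122-730 days, so p = 365/608 = 0.600 and a = (122-30)/335 = 0.275.

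- R = 30%: E = 1 - (0.9067-0.7000)/(0.3567×0.7254) = 0.201; rate = 0.600×0.30 + 0.400×0.201 = 0.260.

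Simulation of 20,000 data sets of 44 subjects under the same assumptions gives the same three values: 21.8%, 7.2% and 26.0%.

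**After every subject has passed the period.** Only early exits remain. With R = 20% and 10% leaving evenly over the period: λ = 0.2231; E = 1 - 0.20/0.2231 = 0.104; rate = 0.90×0.20 + 0.10×0.104 = 0.190. The relative shortfall is about 5%, or (0.200-0.190)×44 = 0.4 of a subject.

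**Deaths.** A subject who dies event-free cannot later have the AE, so keeping that subject in the denominator is correct for cumulative incidence. With assumed period risks of 30% for the AE and 10% for death, true incidence is 0.3567/(0.3567+0.1054) × (1 - 0.70×0.90) = 0.772×0.37 = 28.6%. Kaplan-Meier with deaths censored would target 30%.

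**The two rules at Days 0-30.** Both address the same events with the same cutoff.

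| Event-free subject | 7.10 | 7.9.3.1 |
|---|---|---|
| Withdraws on Day 10 | in denominator | dropped |
| Last contact Day 15 or later | in denominator | in denominator |

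Hypothetically, with 44 enrolled, 6 with the AE and 4 leaving event-free before Day 15, 7.10 gives 6/44 = 13.6% and 7.9.3.1 gives 6/40 = 15.0%.

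**Is 7.9.3.1 the better rule?** At Days 0-30 it happens to do well, because Day 15 is the midpoint: with R = 20% and 10% leaving evenly it gives about 20.0%, against 19.0% under 7.10. Over long windows it runs high, because it keeps early events and drops event-free subjects censored early. As an illustration only, apply it to Days 31-365 with the Day 335 limit, R = 20% and half the entrants censored evenly:

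- events = 0.5×0.20 + 0.5×0.104 = 0.152;
- event-free with contact at or after Day 335 = 0.5×0.80 + 0.5×0.072 = 0.436;
- rate = 0.152/(0.152+0.436) = 25.8%, against 15.2% under 7.10.

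**The case against.** The best defence has three parts.

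First, the sections have different scopes. Section 7.10 is confined to AEs other than MAEs, and it is the only text that defines an AE rate by period. Table 3 is titled for MAEs and major clinical events, and the sentence about any AEs sets no rate and no period. This stands in part. At later time points the rules measure different things: 7.9.3.1 is cumulative from Day 0 and 7.10 is by interval. A reader might infer that the SAP prescribes two widely different rates for the same AE in every period. The documents do not support that: Table 3 has no Day 31-365 row, so the 25.8% above is not a figure the SAP would produce. The direct clash is at Days 0-30. There it is real, because 7.9.3.1 explicitly reaches any AE and nothing ranks the two sections.

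Second, snapshot figures are provisional, and nobody is still awaiting a visit at study close. The accountability table in 7.1.1.2 also shows subjects not yet due, withdrawn or lost; its example goes from 9 to 7 to 2 eligible. This limits the importance but does not correct the rate. That table is organised by visit, and the AE rate itself carries no adjustment.

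Third, the most serious outcomes (death, stroke, paraplegia, MI, renal failure, rupture, conversion) are handled in 7.9.3.1, and no hypothesis is tested. This stands and bears on severity.

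**Conclusion.** The point holds at moderate severity. The 7.10 denominator biases period AE and SAE rates downward, in expectation, whenever a report is cut while subjects are part-way through the period. Under the accrual and hazard assumptions above, the relative shortfall for Days 31-365 is about 27% at month 20 (30% read as 21.8%) and 13% at month 24 (30% read as 26.0%). These snapshots fall at or soon after the end of enrolment, when the effect on this period is large; it disappears for the period once all subjects have passed it, apart from early exits.

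A reader might infer that the final report's AE rates are materially understated. The documents do not support that: follow-up runs to five years or exit, and an assumed 10% exit costs about 0.4 of a subject in 44, well inside the binomial uncertainty. Nor do deaths add to the bias. The primary safety and effectiveness observations do not use the 7.10 rule.

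The SAP should also settle which rule governs AEs. Adopting 7.9.3.1 throughout would exchange a low bias for a high one over the longer windows.

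**What to change.** In 7.10, for both the annual reports and the final report, estimate each period's AE rate among subjects entering it by cumulative incidence (Aalen-Johansen) for the first onset within the period. Censor at withdrawal, last contact or snapshot date, and treat death as a competing event. Kaplan-Meier with deaths censored is not adequate, for the reason shown above.

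Beside each rate, show the numbers entering the period, completing it, and not yet through it.

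In 7.9.3.1, limit the sentence on any AEs to MAEs and the listed major clinical events, or point it to 7.10, so that one rule applies.

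The cost is an SAP amendment under 7.12 and slightly more programming with a standard procedure. It uses the last-contact dates already derived under 7.9.3.1 and onset dates completed under 7.4. AE rates in snapshot reports will be somewhat higher than under the present rule.

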7.11. Health Outcomes Analyses

No Health Outcomes analyses are planned for this study.

7.12. Changes to Planned Analysis

Any changes to planned statistical analyses determined necessary prior to performing the analyses will be documented in an amended Statistical Analysis Plan and approved prior to the analysis. Any other deviations or changes from the planned analyses deemed necessary due to violation of critical

underlying statistical assumptions, data characteristics, or missing data will be clearly described in the clinical study report with justification and rationale.

Version 6.0 of this document incorporated the 'worst case' principle for imaging analyses reporting rule changes requested by the FDA.¹

8. Validation Requirements

All statistical analysis results will be validated. Level I validation will be used for all safety endpoints and efficacy endpoints defined in the Protocol as well as all analysis datasets. Validation methods for each statistical output will be documented in the validation report (GBET 019).

9. References

1. Medtronic work instruction: Aortic Study Reporting Conventions v2.0, based on discussion and agreement with FDA.

10. Statistical Appendices

None.
